### **7.3. Subject Withdrawal Criteria**

A subject may voluntarily withdraw or be withdrawn from the trial at any time for reasons including, but not limited to, the following:

- The subject wishes to withdraw from further participation.
- The subject is significantly noncompliant with the protocol.
- Continuation in the trial would be detrimental to the subject's safety in the opinion of the investigator.

Any subject who wishes to withdraw from the trial may do so at any time without it affecting their medical care. The investigator may withdraw a subject from the trial at any time if it is felt to be in the best interest of the subject.

If a treated subject is discontinued prematurely from further treatment, the investigator must provide an explanation in the subject source records, as well as the eCRF and perform all End of Treatment evaluations according to Visit 15 in [Table 14](#). These subjects should then enter the Follow-up Period, where procedures listed in [Table 15](#) will be performed. In the event that a subject will not continue to be evaluated in the Follow-up Period, the End of Study visit (Visit 24) should be scheduled, and all procedures performed.

In the event that a subject does not return for the Follow-up evaluations, the investigator must make every effort to contact the subject to review all AEs and to determine the reason for dropping out (see [Section 7.3.2](#)).

In the event that a subject discontinues prematurely due to an AE or SAE assessed to be study drug-related, the event should be followed until it resolves (returned to normal or baseline values), stabilizes, or is judged by the investigator to be no longer clinically significant. Follow-up of an AE may also be continued at the request of the Sponsor Medical Monitor.

### **7.3.1. Subject Replacement**

If a subject discontinues for any reason other than toxicity prior to completing 28 days of ELI-002 therapy, a replacement subject will be added to the cohort until 3 subjects per cohort complete 28 days of ELI-002 therapy.

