### 6.1.1. Safety Monitoring

This is an open label, single arm, dose-escalation trial incorporating a 3+3 design. Approximately 18 subjects are planned to be enrolled to evaluate the safety, tolerability and exploratory pharmacodynamic efficacy of ELI-002 at 3 planned dose levels (0.1 mg SC, 0.5 mg SC, 2.5 mg SC) in combination with a fixed dose of Amph-Peptides (700 µg each). Additional cohorts may be added to explore intermediate or higher dose levels. This will be based on the cumulative safety review and preliminary review of efficacy. If additional cohorts are added, this will be documented in a study memo sent to all clinical sites and submitted to IRBs, per IRB guidance.

During the study, ELI-002 will be comprised of 1.4 mg of 2 Amph modified KRAS peptides, Amph-G12D, and Amph-G12R (0.7 mg/peptide) admixed with Amph-CpG-7909 to provide ELI-002 2P. Elicio plans to investigate the use of an Amph-Peptide 7P drug product containing all 7 Amph-Peptides (G12D, G12R, G12V, G12A, G12C, G12S, G13D) admixed with Amph-CpG-7909 (ELI-002 7P) in future clinical trials.

Subjects will receive the initial dose of ELI-002 and be monitored for  $\geq 24$  hours in order to monitor for potential AEs such as CRS. In addition, there will be a 1-week stagger between enrollment of the first subject in a cohort and the subsequent subjects. In the absence of toxicity during the dose-limiting toxicity (DLT) assessment window, ELI-002 will be escalated.

Cohorts will consist of 3 to 6 subjects (the number will depend on whether DLTs are observed). In order to ensure an adequate number of evaluable subjects, up to 6 subjects may be enrolled per cohort even in the absence of a DLT.

Dose escalation from one cohort to the next will be determined by the SMC, and will be based on treatment-emergent AEs, clinical laboratory data, PE findings including vital signs, after all subjects within a cohort have completed 28 days.

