In any cohort, if none of the subjects experience a DLT during the first 28 days following first administration of ELI-002, the dose escalation will occur, and 3 subjects will be enrolled in the cohort at the next dose level. However, if 1 of the 3 or 4 initial subjects in a cohort experiences a DLT, then 3 (or 2, if 4 were originally enrolled) additional subjects will be enrolled at the same dose level. If 2 or more of 3 subjects within a cohort experience a DLT, then this dose will be considered the toxic dose. If only 1 of 6 subjects within a cohort experiences a DLT during the first 28 days of treatment, then the next cohort may begin enrollment. If 2 or more of 6 subjects within a cohort experience a DLT during the first 28 days, then this dose will be considered the toxic dose. The trial may proceed at a lower dose, at a less frequent schedule, or omitting the Amph-CpG-7909 adjuvant while continuing to administer the Amph-Peptides, based on emerging toxicity or pharmacodynamic data until the MTD is determined.

A trial memo will be sent to all sites following each SMC meeting summarizing the decision; if additional cohorts are to be enrolled, the dose level and schedule will be provided.

Safety monitoring is further detailed in the SMC Charter.

The RP2D will be defined in consideration of the MTD (if any), safety data, and pharmacodynamic data. The RP2D will be communicated to all sites in a trial memo following the last SMC cohort review. Once the RP2D is determined, the cohort evaluating the Phase 2 dose will be expanded as needed so that there is safety experience with at least 6 subjects at this dose level.

Please refer to [Section 6.7](#) for management of study drug-related events. DLT Guidelines are specifically detailed in [Section 6.7.3](#).

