## **6.7. Management of Study Drug-Related Events**

### **6.7.1. Temporarily Suspending Treatment Administration**

If a subject meets any of the following conditions within 48 hours prior to the scheduled administration of the trial treatment, treatment administration will be temporarily suspended:

1. To reduce the risk of CRS, subjects will not be given a repeat dose of ELI-002 if they are exhibiting  $T \geq 38^{\circ}\text{C}$  and/or  $\text{IL-6} \geq 500 \text{ pg/mL}$  (cytokine collection, including IL-6, may be performed up to 7 days prior to treatment). In addition, if a subject exhibits  $\text{IFN}\gamma \geq 1000 \text{ pg/mL}$ , the Elicio medical monitor should be contacted for consultation.
2. Adverse event(s) that meet the definition of DLT caused by prior treatment. See [Section 6.7.3](#) for the definition of a DLT; see [Section 12.4](#) for the definition of Common Terminology Criteria for Adverse Events (CTCAEs).
3. Any subsequent dosing in a subject who has experienced Grade  $\geq 2$  CRS/ immune effector cell-associated neurotoxicity syndrome (ICANS)

Investigators must consult the medical monitor to discuss any subjects meeting the above criteria.

In the event the ELI-002 dose is held, the subject should not receive any make up dose and remain on the original protocol schedule (ie, their next dose will be at the next protocol-specified dose if they meet the criteria for dosing). All trial procedures and treatment administration will be resumed as soon as the subject's condition allows or at the investigator's discretion after Sponsor approval.

The trial may proceed at a lower dose, at a less frequent schedule, or omitting the Amph-CpG-7909 adjuvant while continuing to administer the Amph-Peptides, based on emerging toxicity or pharmacodynamic data until the MTD is determined.

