## 12.7. Reporting Adverse Events

All AEs and SAEs will be reported on the appropriate eCRF pages, which will also be the reporting mechanism to Elicio safety/pharmacovigilance. All AEs (related and unrelated) will be recorded from first dose administration until 30 days after the end of study treatment administration. All SAEs (related and unrelated) will be recorded from the signing of the ICF until 30 days after the end of study treatment administration. All SAEs must be reported to Elicio or their designee within 1 business day of the first awareness of the event. The investigator must verify the accuracy of the information recorded on the SAE pages with the corresponding source documents.

Additional follow-up information, if required or available, should all be sent to Elicio or its designee within one business day of receipt and this should be completed on a follow-up SAE form, as well as documented with the original SAE source information and kept with the appropriate section of the subject source records.

Elicio is responsible for notifying the relevant regulatory authorities of certain events. It is the PI's responsibility to notify the Institutional Review Board (IRB) of all SAEs that occur at his or

her trial center in accordance with local IRB requirements. Investigators will also be notified of all unexpected, serious, drug-related events (Suspected Unexpected Serious Adverse Reaction [SUSAR] Reports) that occur during the clinical trial. Each trial center is responsible for notifying its IRB of these additional SAEs in accordance with local requirements. If the clinical site submits to a central IRB, SUSAR reports will be submitted by Elicio or its designee.

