### **MTD definition:**

The MTD is defined as the highest dose level with a DLT incidence  $<33\%$  of cohort subjects.

[figure not shown]
A trial memo will be sent to all sites following each SMC meeting summarizing the decision; if additional cohorts are to be enrolled, the dose level and schedule will be provided.

Safety monitoring is further detailed in the SMC Charter.

The RP2D will be defined in consideration of the MTD (if any), safety data, and pharmacodynamic data. The RP2D will be communicated to all sites in a trial memo following the last SMC cohort review. Once the RP2D is determined, the cohort evaluating the Phase 2 dose will be expanded as needed so that there is safety experience with at least 6 subjects at this dose level.

The Study Flow Chart is presented in Figure 1.

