**Table 7: Planned Summaries of Adverse Events**

AE Type \ Summarize by	Overall Summary [*]	By Cohort and Overall, SOC & PT	Additional Summary
TEAEs	X	X	By Cohort and Overall/Maximum CTCAE grade/SOC/PT By Cohort and Overall leading to study discontinuation
Serious TEAEs	X	X	By Cohort and Overall/relationship to study treatment/SOC/PT
Leading to study treatment discontinuation	X	X	By Cohort and Overall/relationship to study treatment/SOC/PT By Cohort and Overall/PT
Leading to death	X	X	
DLT (Phase 1A only) [#]	X	X	
Related TEAE	X	X	By Cohort and Overall/ leading to study discontinuation
Related TEAEs leading to study treatment discontinuation	X	X	
Cytokine Release Syndrome	X	X	
ICANS		X	
Reactogenicity event	X		By Reactogenicity type, events and toxicity grade

Note: all summary tables will be by Phase, Cohort/Overall.

**Final Analysis  
Statistical Analysis Plan (SAP)**

[\*] All types of AEs with “X” sign will be summarized in one overall summary table of TEAE, including outcome and action taken.

[#] Dose Limiting Toxicities (DLTs) are defined in the Protocol Section 6.7.3. The percentage of subjects having a DLT is based on all treated subjects in each cohort. DLT flag may be added to selected listings of adverse events as appropriate.

Where a subject has the same adverse event, based on PT reported multiple times, the subject will only be counted once at that PT level. Where a subject has multiple adverse events within the same system organ class, the subject will only be counted once at that SOC level.

Any AE with a missing severity based on CTCAE grading, or ASTCT in the case of CRS or ICANS, will be presented in the summary table under the category of “Missing” and will not be imputed. Any AE with a missing relationship to study treatment will be imputed as “Related”. Any AE with a missing “Serious” evaluation will be imputed as “Serious”.

For all AE data captured in the study by the Case Report Form (CRF), by-subject listings will be provided for all AEs, serious TEAEs, TEAEs leading to dose reduction or interruption, DLT and death, respectively.

Cytokine Release Syndrome, ICANS, and reactogenicity to the vaccine data captured in the CRF will be provided in a by-subject listing.

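### Replacement stops at 3 completers although the decision after a DLT is written for 6, and the reported DLT rate counts early leavers as DLT-free

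*Protocol*

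**What the plan says.** **Replacement.** Protocol 7.3.1, repeated in the Synopsis and in 4.6.4, covers subjects who stop before 28 days for reasons other than toxicity: "a replacement subject will be added to the cohort until 3 subjects per cohort complete 28 days of ELI-002 therapy". No higher target is given for an expanded cohort.

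**Expansion and decision.** Under Protocol 6.1.1, when one of the first 3 or 4 subjects has a DLT, "then 3 (or 2, if 4 were originally enrolled) additional subjects will be enrolled at the same dose level". The next cohort may open under this condition: "If only 1 of 6 subjects within a cohort experiences a DLT during the first 28 days of treatment". Two or more of 6 makes the dose toxic. SAP 8.1 repeats these rules. No other denominator is covered after expansion.

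**Evaluability.** Protocol 6.1.1 also says: "In order to ensure an adequate number of evaluable subjects, up to 6 subjects may be enrolled per cohort", even without a DLT. Neither Protocol 13.2.2 nor SAP 11 defines evaluable for DLTs. The only evaluable sets are one for disease response, which SAP 14 drops, and one for pharmacodynamics and biomarkers.

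**Denominators.** The footnote to the adverse-event summary table in SAP 13.7.1 states: "The percentage of subjects having a DLT is based on all treated subjects in each cohort". SAP 8.1 states: "The MTD is defined as the highest dose level with a DLT incidence" under 33% of cohort subjects, as does Protocol 6.7.3. Neither says which cohort subjects count.

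**The concern.** The MTD and RP2D are primary endpoints of a first-in-human trial. A 3+3 decision rests on how many subjects were observed through the DLT window, and that number matters most after a DLT has occurred. Here the replacement rule secures 3 such subjects and the decision rule needs 6.

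The final table uses yet another basis. A subject who leaves without a DLT after 1 of the 4 doses in the window counts the same as a subject who received all 4. The reported DLT rate can then be lower than the rate on which the dose decision was made, and a reader of the study report could not reconcile the two from the percentage alone.

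**Working it through.** **Inputs.** Replacement target 3 (Protocol 7.3.1); additions 3, or 2 if 4 were enrolled, and decision size 6 (Protocol 6.1.1); MTD limit below 33% (Protocol 6.7.3); all-treated denominator (SAP 13.7.1). Doses fall on Days 57, 64, 71, 78 and 92 (Protocol Table 12), that is 0, 7, 14, 21 and 35 days after the first, so 4 fall inside the 28-day window. The documents give no DLT or dropout rate. The DLT rate p and the loss L per added subject are assumptions.

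**1. The plan's own figures.** 3 cohorts × 6 = 18 subjects, as stated. 1/6 = 16.7% is below 33% and 2/6 = 33.3% is not, so the 3+3 rule and the MTD definition agree when all 6 are evaluable. 1/5 = 20.0% and 1/4 = 25.0% are also below 33%, but no rule is written for them.

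**2. How a short cohort arises.**
- Three are added after a DLT and one or two leave early for non-toxicity reasons. If 3 subjects in the cohort have completed 28 days, nobody is replaced. Six are treated and 5 or 4 are evaluable.
- It can also happen with no loss among the added subjects. Four are enrolled, 1 leaves early and 3 complete, one of them with a DLT. That subject can complete because, when a dose is held, "the subject should not receive any make up dose and remain on the original protocol schedule" (Protocol 6.7.1). The target of 3 is met, and because 4 were enrolled only 2 are added. Six are treated and 5 are evaluable. The text does not say whether this is 1 of 6 or 1 of 5.

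**3. How often, among expanded cohorts.** The chance that at least one added subject is lost is 1 − (1 − L)^m, with m subjects added.
- m = 3: L = 5%, 10%, 20% gives 14.3%, 27.1%, 48.8%.
- m = 2: 9.8%, 19.0%, 36.0%.

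These are upper bounds, because replacement still operates while fewer than 3 have completed. They also apply only to cohorts that expand. At p = 20% the chance of exactly 1 DLT in 3 is 3 × 0.2 × 0.8² = 38.4%, so 27.1% becomes about 10% of all cohorts.

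**4. Effect on escalation, with p = 40% and losses counted as DLT-free.**
- 3 then 3: (1 − p)³ + 3p(1 − p)² × [1 − p(1 − L)]³ = 0.216 + 0.432 × [1 − 0.4(1 − L)]³. For L = 0, 5%, 10%, 20%: 30.9%, 31.9%, 32.9%, 35.2%.
- 4 then 2: (1 − p)⁴ + 4p(1 − p)³ × [1 − p(1 − L)]² = 0.1296 + 0.3456 × [1 − 0.4(1 − L)]². For the same L: 25.4%, 26.2%, 27.1%, 28.9%.

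At 5% to 10% loss the rise is 1.0 to 2.0 points (3 then 3) or 0.8 to 1.7 points (4 then 2). Both formulas cover losses among added subjects only. They assume that every loss hides any DLT and that short cohorts may escalate. For scale, if one of 3 added subjects were lost for certain and the cohort still escalated on no further DLT, the 3-then-3 figure would be 0.216 + 0.432 × 0.6² = 37.2%.

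**5. Effect on the table.** Three are enrolled, 1 leaves and is replaced, and 1 of the 3 evaluable has a DLT. Three are added, with 1 further DLT. Evaluable: 2/6 = 33.3%, toxic. Tabulated: 2/7 = 28.6%. Likewise 1/5 = 20.0% evaluable is shown as 1/6 = 16.7%.

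**The case against.** The decision-maker is not missing. The SMC determines escalation after all subjects in the cohort have completed 28 days, reviews all available safety data, and is not obliged to escalate after 1 of 6. Subjects who stop treatment should continue in follow-up, and Protocol 12.7 states: "All AEs (related and unrelated) will be recorded from first dose administration until 30 days after the end of study treatment administration". For someone who stops after the first dose, that period covers the 28-day window. DLT status will therefore often be known, and what is lost is exposure. Up to 6 subjects may be enrolled at the outset, and the RP2D needs safety experience in at least 6. The SMC Charter, which is not among the documents, may define evaluability. Counts, a by-subject DLT listing and reasons for discontinuation will be reported beside the percentage.

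All of this stands, and it is why the effect is modest. It does not supply the missing rule or denominator: the RP2D requirement does not say evaluable, and the SAP adopts no charter definition.

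A reader might go further and infer that the plan lets short cohorts escalate. The text does not support that. Read literally, 1 of 4 or 1 of 5 does not satisfy the 1-of-6 condition, which is the cautious outcome. The escalation figures above assume the opposite and are a bound, not a prediction.

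**Conclusion.** The concern holds as a gap in the rules and a distortion in reporting. Two stated rules do not fit together, so an expanded cohort can reach the SMC with 4 or 5 evaluable subjects and no written rule for that number. Separately, the all-treated denominator can show a DLT rate below 33% for a dose already toxic under 3+3.

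It is tempting to conclude that the SAP percentage would set the MTD and so reverse a toxic-dose finding. The documents do not say so. No section makes that percentage the basis of the MTD, and the 3+3 rule and the SMC govern escalation.

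At an assumed 40% DLT rate and 5% to 10% loss among added subjects, escalation rises by at most 1 to 2 points. That is an upper bound for such losses, under the two assumptions stated with the formulas. All rates are assumptions, and a definition in the SMC Charter would narrow the point to aligning the SAP with it.

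**What to change.** **Now, whatever the enrolment status.** Define a DLT-evaluable set in SAP 11: subjects who had a DLT, or who completed the 28-day window with a stated minimum of the 4 scheduled doses. Match the SMC Charter if it already has a definition. Report DLTs per cohort on both the evaluable and the treated denominators, and state that the MTD definition (Protocol 6.7.3, SAP 8.1) is read on the evaluable set.

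**Only if cohorts are still enrolling.** Amend Protocol 7.3.1, with the Synopsis and 4.6.4, to replace until 3 subjects, or 6 after a DLT, are evaluable. Let the option of adding only 2 apply only when all 4 initial subjects are evaluable. This part is probably too late: the Synopsis planned last enrolment for 2Q2023, and the SAP is the final-analysis version, citing a protocol dated August 2023.

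**Cost.** One analysis set and one extra table column; if enrolment is open, an occasional additional subject in an expanded cohort.

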### **7.3.2. Subjects Lost to Follow-up**

If a subject is lost to follow-up, every attempt must be made to contact the subject and to determine the reason for dropping out. If the subject cannot be reached after three documented attempts over a reasonable amount of time, a certified letter must be sent to the subject asking them to contact the trial center for follow-up. Only after all above documented attempts will a subject be considered lost to follow-up.

## **8. TREATMENT OF SUBJECTS**

### **8.1. Concomitant Medications**

Subjects should receive medication appropriate to their health condition during the entire trial. All concomitant medications during the length of the trial, including screening, will be documented in the subject source record and in the appropriate electronic case report form (eCRF) page.

#### **8.1.1. Prohibited Concomitant Medications**

The following concomitant medications should not be used during study drug administration and are criteria for permanent stopping of the trial treatment administration for an individual subject

- Growth factors (except erythropoietin). The effect of growth factor administration on expansion and persistence of ELI-002 is unknown.
- Corticosteroids and other immunosuppressive agents except as needed for management of safety events. Systemic immunosuppressive agents should not be used while in the trial, except if needed for counteracting an AE, eg, cytokine release syndrome. However, the use of corticosteroids for anti-allergic reaction/symptoms, eg, pre/post tumor imaging (contrast product); topical and inhaled steroids are permitted.
- Cytotoxic agents and any other cancer therapy
- Investigational products/devices

### **8.2. Treatment Compliance**

All subjects are expected to be fully compliant throughout the trial (see [Section 6.7.2](#)).

Subjects will receive SC injections of ELI-002 by qualified site staff who are under the supervision of the investigator or designee.

Treatment administration will be recorded on the eCRF.

### **8.3. Randomization and Blinding**

ELI-002 is an open-label, Phase 1 trial with a single arm. Treatment will not be blinded and there will not be randomization as part of this study.

## 9. TRIAL DRUG MATERIALS AND MANAGEMENT

### 9.1. Trial Drug

ELI-002 is an investigational product consisting of 2 drug products:

1. A mixture of lipid-conjugated peptide-based antigens (amphiphilic peptides, referred to as ‘Amph-Peptides’). During the study, the Amph-Peptide mixture (Amph-Peptides 2P) will be comprised of 1.4 mg of 2 Amph modified KRAS peptides, Amph-G12D, and Amph-G12R (0.7 mg/peptide). Elicio plans to investigate the use of an Amph-Peptide 7P drug product containing all 7 Amph-Peptides (G12D, G12R, G12V, G12A, G12C, G12S, G13D) in future clinical trials.
2. A lipid-conjugated immune-stimulatory oligonucleotide (‘Amph-CpG-7909’)

The ELI-002 admixture is prepared by combining the separately provided products in a diluent prior to dosing. The KRAS Amph-Peptides are provided in 5.0 mM, pH 4.5 acetate buffer in a 2-mL glass vial. The Amph-CpG-7909 is provided in water for injection (WFI) in a 2-mL glass vial. These 2 drug products will then be provided to the clinical pharmacy for combination with 10X PBS (phosphate buffered saline) on a dose-by-dose basis at the proper ratio for administration to the subject as a drug product admixture. For further details, refer to the Product Manual.

In the event of toxicity after immunization period doses, Amph-Peptides without Amph-CpG-7909 adjuvant may be administered during the booster period.

The Product Manual will provide instructions for the admixing procedure as well as storage instructions.

